Intro: as the interview progresses the nurse will gain access to the various screens concerning the adverse events described by the patient at any time during the telephone conversation; moreover, at this stage of the interview, the nurse will check for any other AEs that may not have been mentioned before.

Since the last interview, since starting taking Sutent® (for the first call), have you had any discomfort, or have you experienced unexpected effects related to your Sutent® treatment other than those we have already discussed? Yes No

- If Yes, [\[Go to AE information collection questionnaire\]](#)
 - ↳ Once the patient has finished describing the AE: Have you experienced any other discomfort or adverse reactions?
- If not, check for the absence of AEs: Do not hesitate to report any problems you might encounter, even the mildest such as for example:
 - Changes to skin, nail or hair
 - Digestive disorders
 - Breathing difficulties
 - Heart disorders or change in blood pressure
 - Mouth or gum problems
 - Other adverse events such as tiredness or fever, etc.

Ongoing grade 3 / 4 AE: Recommendation for temporary interruption of Sutent® treatment pending oncologist's medical opinion: Yes No

- ↳ If Yes, In this situation, I recommend that you temporarily interrupt your Sutent® treatment until further notice. Your oncologist will be alerted and his/her medical opinion requested. We will contact you to inform you of his/her decision.

Activities of daily life: preparing meals, shopping, using a telephone, paying.

Major daily activity: Showering, dressing and undressing, eating, going to the toilet.

Instruction: any report of a grade 3 or 4 AE, except for a biological AE, will trigger an email alert for the oncologist + Level 3 TEC. Other alerts are generated on a case by case basis for certain grade 2 AEs.

Table 8 - AE / Grade / Action look-up table for Sutent®-related AEs

Adverse event	CTCAE grade estimation	Recommendations and Actions to implement
Skin toxicity		

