- Anaemia	
 - STANDARD Man: 13 – 17 g/dL; Woman: 12 – 15 g/dL - Grade 1: < 10 g/dL (6.2 mmol/L or 100g/L) - Grade 2: 8 – 10 g/dL (6.2- 4.9 mmol/l or 100-80g/L) - Grade 3: <8 g/dL (\leq 4.9 mmol/L or 80 g/L) 	
 - Grade 1: no action - Grade 2: oncologist email alert - Grade 3: patient contacts oncologist
- Haematuria		
 - Alert oncologist by email as soon as haematuria observed
- Neutropenia	
 - Grade 0: 1,8 – 7 *10⁹/L - Grade 1: 1,5 – 1,8 *10⁹/L - Grade 2: 1,0 – 1,5 *10⁹/L - Grade 3: 0,5 – 1,0 *10⁹/L (1000 mm³ + fever) - Grade 4: <0,5 *10⁹/L 
Presence of fever? Yes (Grade 2 > 3, 3 > 4)
	
 - Grade 1: no prescription of GCSF, talk to oncologist at next visit - Grade 2: alert oncologist in report - Grade 3: alert oncologist by email; if fever: Fever management advice + rapidly contact oncologist by phone - Grade 4: rapidly contact oncologist by phone
- Thrombocytopenia	
 - STANDARD > 150 * 10⁹/L - Grade 1: 75,0 – 150 *10⁹/L - Grade 2: 50,0 – 75,0 *10⁹/L - Grade 3: 25,0 – 50,0 *10⁹/L 	
 - Grade 1: no action recommended - Grade 2: oncologist email alert - Grade 3: rapidly contact oncologist + alert oncologist by email
- Increased creatininaemia	
 - STANDARD: 7 to 13 mg/L - Grade 1: 1 to 1.5* previous value - Grade 2: 1.5 to 3* previous value - Grade 3: 3 to 6* previous value - Grade 4: >10 * previous value 	
 - No grade 1 event, recommend drinking to avoid dehydration. Creatinine drops during the 2 weeks of break. - Grade 2: oncologist email alert - Grade 3: rapidly contact oncologist + alert

	
 - 	oncologist by email
- Hypothyroidism	
 - Grade 1: TSH 5 to 10 µU/mL - Grade 2: TSG > 10 µU/mL 	
 - Grade 1: asymptomatic, does not require management - Grade 2: general practitioner, additional tests to implement appropriate treatment
- Hyperthyroidism	
 - Grade 1: TSH 0.30 to 0.10 µU/mL - Grade 2: TSH < 0.10 µU/mL 	
 - Grade 1: asymptomatic, does not require management - Grade 2: general practitioner, additional tests to implement appropriate treatment
Infectious problems		

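### The nurse look-up table leaves creatinine above 6 and up to 10 times the previous value, and platelets below 25 × 10⁹/L, with no grade and no action, and gives creatinine above 10 times a grade but no action

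*Protocol*

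**What the plan says.** Table 8 in Protocol Appendix 7, section D.5, pairs each adverse event with a column headed "CTCAE grade estimation" and a column of actions for the platform nurse.

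- **Increased creatininaemia.** The upper bands are "Grade 3: 3 to 6* previous value" and then "Grade 4: >10 * previous value". The action column ends at grade 3.
- **Thrombocytopenia.** The last band is "Grade 3: 25,0 – 50,0" (× 10⁹/L). The last action is "Grade 3: rapidly contact oncologist + alert oncologist by email". Neither column has a grade 4 line.

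Two general rules in section D.5 sit above the table:

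- The alert instruction: "any report of a grade 3 or 4 AE, except for a biological AE, will trigger an email alert for the oncologist".
- A yes/no prompt: "Ongoing grade 3 / 4 AE: Recommendation for temporary interruption of Sutent® treatment pending oncologist's medical opinion". If the nurse ticks yes, the patient is told: "Your oncologist will be alerted and his/her medical opinion requested".

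The definitive grade belongs to the participating physician (Protocol 7.3.1 and 8.9.3).

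**The concern.** A triage table should respond at least as strongly to a worse value as to a milder one. In these two rows it stops responding just beyond grade 3.

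The row-level action carries more weight for laboratory events than for symptoms, because the automatic email is switched off for biological events. The remaining written real-time route, the D.5 prompt, starts from a grade 3 or 4 rating. A value with no printed grade triggers neither the row nor the prompt.

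What is at stake is timely contact with the oncologist about possible severe thrombocytopenia or renal deterioration on sunitinib. The nurses are expected to meet such results: section D.3.4 asks patients to have their examination results to hand and prompts an adverse event report that depends on them.

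**Working it through.** No figure in the plan needs reproducing. The check is whether the printed bands cover the scale, and which written routes each value reaches. Range ends are taken as inclusive.

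**Step 1. Coverage, from Table 8**

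| Creatinine (multiple of previous value) | Grade | Action in row |
|---|---|---|
| 1 to 1.5 | 1 | advice on fluids |
| 1.5 to 3 | 2 | email to oncologist |
| 3 to 6 | 3 | rapid contact plus email |
| above 6, up to 10 | none | none |
| above 10 | 4 | none |

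| Platelets (× 10⁹/L) | Grade | Action in row |
|---|---|---|
| 75 to 150 | 1 | none advised |
| 50 to 75 | 2 | email to oncologist |
| 25 to 50 | 3 | rapid contact plus email |
| below 25 | none | none |

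Applied to single values:

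- Creatinine at 6 times gives grade 3. At 6.1, 6.5, 8 and 10 times it gives no grade. At 10.1 times it gives grade 4.
- Platelets of 25 give grade 3. Counts of 24, 20 and 10 give no grade.

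**Step 2. Width of the creatinine gap in mg/L**

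The row's own standard range is 7 to 13 mg/L. The ungraded interval runs from above 6 × previous value up to 10 × previous value:

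- previous 7: above 6 × 7 = 42, up to 10 × 7 = 70
- previous 10: above 60, up to 100
- previous 13: above 6 × 13 = 78, up to 10 × 13 = 130

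**Step 3. Written real-time routes to the oncologist**

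| Value | Row action | Automatic email | D.5 prompt |
|---|---|---|---|
| Creatinine 5 times | yes | no (biological) | yes, grade 3 |
| Creatinine 8 times | no | no | only if the nurse assigns a grade herself |
| Creatinine 11 times | no | no (biological) | yes, grade 4 |
| Platelets 30 | yes | no (biological) | yes, grade 3 |
| Platelets 20 | no | no | only if the nurse assigns a grade herself |

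The D.5 column assumes the event is still ongoing at the call. The order is inverted in both rows: the milder value has two written routes, and the worse one has none that the table itself supplies.

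**Step 4. Is this an intended limit of the table?**

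The neutropenia row in the same block prints an open-ended grade 4 with its own action, rapid telephone contact with the oncologist. The nurse's adverse event form (Table 7) also offers grade 4. So the script does expect grade 4 laboratory events to be graded and acted on. The final row, for other events, refers the nurse to CTCAE, but it covers events that the table does not list, and both of these are listed.

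**The case against.** The strongest reply is that Table 8 is an aid to judgement. Nothing says that the CATI system computes a grade from it. The nurse chooses the grade in Table 7, under a CTCAE v4.03 header, and CTCAE is available on the study website. Seeing 25 to 50 marked as grade 3, a trained nurse told of a count of 20 would probably choose grade 4, and the D.5 prompt, which does not exclude biological events, would then apply. This stands, and it is why the point is limited to the written rule. It does not remove the gap, because escalation at the severe end then rests on the nurse supplying what the table omits.

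Other safeguards also stand. Platform physicians can assist the nurses (Protocol 8.2). A call summary and adverse event sheets go to the physician (Appendix 7, sections F and G). Patients are told at the first call to contact their oncologist or the emergency services directly for a serious event (section D.2.1). Usual medical care continues unchanged. Table 6 has no numeric result field, so the bands matter only when the patient states a value.

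A reader might infer three stronger things, none of which the documents support:

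- **That these rows are uniquely defective.** Vomiting goes from 3–5 episodes to more than 6, and diarrhoea from 4–6 stools to more than 7. Hypertension defines grade 4 but lists actions only for lower grades.
- **That such patients have no protection.** The safeguards above say otherwise.
- **That the primary endpoint is misclassified.** The physician sets the definitive grade under CTCAE v4.03.

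Finally, the CTCAE cut-points are not in the documents. From the table alone, grade 4 could start above 6 times or grade 3 could extend to 10. Only the discontinuity is certain.

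**Conclusion.** The gap is real and worth correcting. Creatinine above 6 and up to 10 times the previous value and platelets below 25 × 10⁹/L have neither grade nor action. Creatinine above 10 times has a grade but no action in its row, although its grade 4 label still leads to the D.5 prompt. The two ungraded ranges can miss written real-time escalation unless the nurse assigns grade 4 on her own judgement.

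This is a patient-safety and triage weakness of modest size. Its frequency cannot be estimated, because the documents do not say how many patients would report such values by telephone, and they may be few. The conclusion rests on the bands as printed and on a literal reading of the script. The row lists run in order, and in the platelet row both columns stop at the same grade, so text lost in conversion is an unlikely explanation.

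**What to change.** In the nurse script and the CATI look-up:

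1. Check both rows against CTCAE v4.03.
2. Subject to that check, start creatinine grade 4 where grade 3 ends (above 6 times the previous value) and add platelet grade 4 below 25 × 10⁹/L. If the check gives other cut-points, use those, but leave no gap between bands and no uncovered severe end.
3. Give every grade 4 value in both rows an action at least as urgent as the grade 3 action in the same row: rapid contact with the oncologist plus an email alert.

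The cost is an edit to two rows, a re-test of the look-up, a short note to the nurses, and validation by the Scientific Committee, which already validates the call scenario (Protocol 12.2). Any amendment step that applies would be added. The statistical analysis does not change.

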14.8. Appendix 8: Adverse event report form

**Non-interventional study:
Adverse event report form**

For Pfizer use

AER number

Date reported to Pfizer

Enter all dates in DD/MM/YYYY format

A	6	1	8	1	2	1	3
---	---	---	---	---	---	---	---

PROTOCOL / STUDY NUMBER

0	0		
---	---	--	--

CENTRE NO.

--	--	--	--	--	--	--	--

PATIENT ID/RANDOMISATION NUMBER

Protocol title: RENACALL STUDY: Evaluation of the impact of a therapy management platform on the management of patients suffering from advanced/metastatic renal cell carcinoma and receiving first line treatment with sunitinib, versus standard follow-up

Initial report Follow-up report

Country in which the event occurred:

Patient data

Age: _____

Height: _____ cm

Ethnic origin:

Man Woman

Weight: _____

kg

Local regulations forbid asking the question

If the patient is deceased: Date of death: ____/____/____ Cause of death: _____

Autopsy performed YES NO UNKNOWN

If yes, what is the cause of death as determined by the autopsy: ____/____/____

Patient's history

None Unknown

Note any relevant medical history below. Include any other diseases present at the time of the event, along with pre-existing medical conditions. If there is not enough space, use additional copies of the page.

Unknown

Disease (specify)		Onset date	End date	Tick if disease is current	Relevant information including surgical procedures and dates		
		____/____/____	____/____/____				
		____/____/____	____/____/____				

**Test drug,
Dosage form,
route of
administration**

Tick if
Pfizer
product

Assay

Units

Frequency

Start date

End date

Tick if
current drug

____/____/____

____/____/____

Concomitant drugs

None Unknown

Report below any concomitant medicines taken during the 2 weeks preceding onset of the event. Exclude any medicines taken only more than 2 weeks prior to onset of the event, along with any medicines taken to treat the event, or taken after onset of the event. If you do not have enough space, use several copies of this page.

Drug name
(registered trademark and
INN)

Indication

Route of
administration

Start date

End date

Tick if
current drug

____/____/____

____/____/____

____/____/____

____/____/____

**Relevant additional
examinations**

Note only those additional examination results that are relevant to the event(s); for example, laboratory analysis and imaging result. If you do not have enough space, use several copies of this page.

Examination	Date	Result	Units	Normal values		Comments
				Lower limit	Upper limit	

Non-interventional study: Adverse event report form

For Pfizer use

AER number

Enter all dates in DD/MM/YYYY format

A 6 1 8 1 2 1 3
PROTOCOL / STUDY NUMBER0 0
CENTRE NO.

PATIENT ID/RANDOMISATION NUMBER

SERIOUS ADVERSE EVENTS (if more than 2, use additional copies of this page)

If known, specify the diagnosis rather than the signs and symptoms.

Adverse event: _____	Adverse event: _____	
Onset date: ____ / ____ / ____	Onset date: ____ / ____ / ____	
Is the event serious? :  YES  NO If yes, specify the seriousness criteria below:	Is the event serious? :  YES  NO If yes, specify the seriousness criteria below:	
Seriousness criterion (several choices possible):  Caused death  Life-threatening  Hospitalisation/extension of hospitalisation  Permanent or major invalidity or disability  Anomaly / congenital malformation  Medically significant event	Seriousness criterion (several choices possible):  Caused death  Life-threatening  Hospitalisation/extension of hospitalisation  Permanent or major invalidity or disability  Anomaly / congenital malformation  Medically significant event	
Progress at the time of this report, or at the time of death:  Recovered Recovery date: ____ / ____ / ____  Recovered with sequelae  Recovering  Not recovered  Unknown	Progress at the time of this report, or at the time of death:  Recovered Recovery date: ____ / ____ / ____  Recovered with sequelae  Recovering  Not recovered  Unknown	
Is there a reasonable possibility that the event was linked to the test drug:  YES  NO If yes, specify the test drug:	Is there a reasonable possibility that the event was linked to the test drug:  YES  NO If yes, specify the test drug:	
Is there a reasonable possibility that the event was linked to a concomitant drug:  YES  NO If yes, specify the concomitant drug:	Is there a reasonable possibility that the event was linked to a concomitant drug:  YES  NO If yes, specify the concomitant drug:	
Last action undertaken during the event(s), specify the name of the drug:  Interruption (temporary, permanent, or delayed)  Dose reduction  Dose increase  Dose unchanged  Unknown  Not applicable	  Interruption (temporary, permanent, or delayed)  Dose reduction  Dose increase  Dose unchanged  Unknown  Not applicable	  Interruption (temporary, permanent, or delayed)  Dose reduction  Dose increase  Dose unchanged  Unknown  Not applicable
Did an AE/SAE re-appear during re-administration of the drug?  Yes  No  Unknown  Not applicable		
If yes, which AE(s)/SAE(s):		
Event history (narrative): Please provide any relevant information concerning this event and that is not reported in another field of this form (circumstances, chronology; diagnosis and symptomatic treatment). If you do not have enough space, use several copies of this page.		
Centre employee in charge of notification for the centre: Last and first names IN BLOCK CAPITALS _____ Date _____		
Address: _____ Street _____ Town _____ Post code _____ Country _____		
Phone no.: _____ Fax no.: _____ Email: _____		
Investigator's name if different: _____ Date investigator (or notifier) informed: _____ DD ____ MMM ____ YYYY		
Investigator's signature: _____		

14.9. Appendix 9: "Morisky" patient self-questionnaire (Sutent® treatment compliance)**Questionnaire concerning your treatment**

(tick a single answer per question)

- | | Yes | No |
|--|--------------------------|--------------------------|
| • Do you ever forget to take your medicines? |  |  |
| • Do you even have problems remembering to take your medicines? |  |  |
| • When you feel better, do you sometimes stop taking your medicines? |  |  |
| • Sometimes, if you feel worse after taking your medicines, do you stop taking them? |  |  |

Additional question concerning adverse events

- | | Yes | No |
|--|--------------------------|--------------------------|
| • When you suffer an adverse event, do you ever reduce or adapt the treatment? |  |  |

14.10. Appendix 10: "Physician" call centre satisfaction evaluation questionnaire

- Collected via the e-CRF at the end of the last follow-up visit (end-of-study visit)
 - 3 dimensions evaluated

Very satisfied	Satisfied	Not very satisfied	Not satisfied	No opinion
----------------	-----------	--------------------	---------------	------------

Satisfaction concerning advice

- Do you consider that your patient's support by a call centre helped reduce the number and/or frequency of grade 3 and 4 AEs thanks to the advice provided?
- Do you consider that your patient's support by a call centre helped improve treatment compliance?
- How satisfied or dissatisfied are you with your patient's change in quality of life thanks to the advice provided by the call centre?

Satisfaction concerning management

- Do you consider that your patient's support by a call centre helped reduce your workload?

Overall satisfaction

- Overall, how satisfied or dissatisfied are you with the management of your patient by the call centre?

Do you have any comment to make

₁ Yes ₀ No

Where possible, would you wish to continue this type of support?

- ₁ yes, absolutely
 ₂ maybe
 ₃ not really
 ₄ not at all
 ₅ no opinion

14.11. Appendix 11: "Patient" call centre satisfaction evaluation questionnaire

- Collected via a self-questionnaire at the end of the last follow-up visit (end-of-study visit)
- 4 dimensions evaluated

Very satisfied	Satisfied	Not very satisfied	Not satisfied	No opinion
----------------	-----------	--------------------	---------------	------------

Satisfaction concerning advice

- How satisfied or dissatisfied were you with the prevention advice you received from the call centre to avoid serious adverse events associated with your Sutent® treatment?
- How satisfied or dissatisfied were you with the treatments recommended by the call centre to reduce / limit the side effects associated with your Sutent® treatment?
- How satisfied or dissatisfied were you with the call centre's ability to direct you to a general practitioner / oncologist when your situation required it?

Satisfaction concerning management

- How satisfied or dissatisfied were you with the explanations given by the call centre concerning your disease, your treatment and/or their side effects?

Satisfaction concerning the service

- Were you satisfied or dissatisfied with the interest shown by the call centre nurses in what you were saying, in your problems and in yourself?
- Do you consider that the frequency, duration and number of follow-up calls that you received from the call centre were adapted to your situation?
- How satisfied or dissatisfied were you with the availability of the call centre nurses via the freephone number provided - ease of contacting the freephone number, answer speed, recall if message on voice mail, wait time, etc.?

Overall satisfaction

- Overall, how satisfied or dissatisfied are you with the support you received by the call centre supporting you in management of your Sutent® treatment?
-

Do you have any comment to make

₁ Yes ₀ No

Where possible, would you wish to continue this type of support?

₁ yes, absolutely

- 2 maybe
- 3 not really
- 4 not at all
- 5 no opinion

Would you recommend this type of follow-up to a friend or family member?

- 1 yes, absolutely
- 2 maybe
- 3 not really
- 4 not at all
- 5 no opinion

Do you consider that you needed the advice and actions proposed by the call centre throughout the duration of your participation in this study?

Yes No

If not: When do you think you became independent concerning management of your treatment and its side effects? _____

1. VERSION HISTORY

Version	Amendments	Date
V6.3	Final version	06/02/2019

The therapeutic management of patients within the facility will not be changed by the study and will follow the recommendations in the SmPC. Patients who are included will receive an additional intervention with follow-up from the treatment management telephone call center. Management through the treatment management telephone call center involves regular telephone calls (cf. Figure 1) in order to support the patient in his/her home management with sunitinib treatment under real life conditions (prevention, advice and directing patients towards options available).

[figure not shown]

Figure 1. Plan of telephone calls

■ **Populations**

- **Population of Participating doctors**

The study will be proposed to 58 doctors throughout 50 Mainland France oncology centers identified as treating patients suffering from metastatic/advanced renal cell carcinoma. It is planned to identify 20 to 25 doctors liable to take part in the study.

These centers will be selected by the Pfizer Company. They will need to have a number of patients which meet the eligibility criterion which is sufficient to be included (approximately 10 patients per year) and not to have a routine management call center already in place in their facility.

- **Patient Population**

It is expected to recruit 100 patients for this study, i.e. approximately 10 per center. The patients must meet the following inclusion and non-inclusion criteria.

Table 1: Patient eligibility criteria

Inclusion criteria	Non-inclusion criteria

 - Men or women, aged 18 years old or over; - Patients suffering from advanced and/or metastatic renal cell carcinoma treated first line with sunitinib according to the SmPC recommendations; - Starting Sutent® in accordance with the SmPC recommendations (50 mg/day, dosage regimen 4/2); - Resolution (grade ≤ 1 according to CTCAE version 4.03 dated June 2010) of all the acute toxic effects due to previous treatment with radiotherapy or a surgical procedure before starting sunitinib; - Patients who can be followed up for 6 months; - Patients of childbearing potential who must be using a method of contraception throughout the period of treatment with sunitinib and for a minimum of 28 days after stopping treatment with sunitinib; - Patients who have given their signed consent; - Patients belonging to a social security system. 	
 - Patients taking part in a clinical trial during treatment with sunitinib; - Patients managed by a home hospitalization service during treatment with sunitinib; - Patients taking part in therapeutic education programs or receiving a nurse consultation or any other significant support for treatment liable to impact on the management of adverse effects; - Patients suffering from untreated and/or symptomatic cerebral metastases before beginning sunitinib; - Patients who refuse to allow their personal data to be used; - Patients with an ECOG performance index at inclusion > 2; - Patients with a serum creatinine of > 1.5 times the upper limit of normal; - Patients with bilirubin concentrations > 2 mg/dl, aspartate transaminase (AST) or alanine transaminase (ALT) levels > 2.5 times the upper limit of normal value or > 5 times the upper limit of normal in the presence of liver metastases when sunitinib treatment is started; - Patients who are staff members of the center involved in the study or are personal friends to a member of the center directly involved in the management of the study, or patients who are employed by Pfizer and are involved in the conduct of the study.

■ Data collection

The data collected during the inclusion and follow-up visits are shown in Table 2:

Table 2: Data collected during the RENACALL study inclusion and follow-up consultations

	V0: Inclusion T0	V1: end of cycle 1 W6	V2: end of cycle 2 W12	V3: end of cycle 4 W24
Data completed by the doctor (in the eCRF)				
Meeting the eligibility criteria	x			
ECOG performance index	x	x	x	x
Karnofsky index/Heng criterion risk score	x			
Sociodemographic features	x			
History of the disorder/description of the renal cell carcinoma	x			
Past medical history and comorbidities	x			
Tumor assessment/ Disease assessment		x	x	x
Data from the laboratory, histological or metastatic assessments	x	x	x	x
Conditions for the use of Sunitinib	x			
Change in the conditions of use for Sunitinib		x	x	x
Concomitant treatments	x	x	x	x
Pharmacovigilance data		x	x	x
Medical procedures (telephone calls, consultations, hospitalizations), both planned and unplanned		x	x	x
Issuing of support materials for treatment with sunitinib	x	x	x	x
Data completed by the patient (self-completed questionnaire)				
Adherence to treatment (4 item Morisky questionnaire)		x	x	x
Data completed by the doctor (in the eCRF) and patient (self-completed questionnaire)				
Satisfaction with the telephone call center				x

The following data will be collected by the nurses during the telephone calls (recorded by a CATI - Computer-Assisted Telephone Interview) system:

- Number of attempts and outcome of the call;
- General patient health;
- Administration of treatment;
- Tolerability and onset of AEs (description of the AE: intensity, symptoms, impact on the patient, investigations, action instituted);
- Proposed action.

The investigator characteristics will be obtained from an extraction from the database provided by Pfizer.

